11.1.1. Viral Shedding

For viral shedding in nasopharyngeal swab specimen based on RT-qPCR, the actual values and change from baseline for viral shedding, percentage of patients with positive/negative viral shedding, duration of viral shedding, and AUC of viral levels will be summarized by each treatment group at each scheduled visit using descriptive statistics (n, mean, SE, minimum, median and maximum) or frequency tables. Mean (\pm SE) viral load titer will be plotted for each scheduled time point in log scale. If EOT result is available and the result from patient whose viral titer result at Day 28 is greater than or equal to negative threshold, the result of EOT visit will be included in summary table (the actual values and change from baseline for viral shedding, percentage of patients with positive/negative viral shedding).

The following rules present how viral titers will be treated in descriptive summary and AUC calculation, and categorized to Positive or Negative. AUC will be displayed to two decimal places. The analysis will be based on the 2.33 log₁₀cp/mL. Additionally negative threshold for 3 and 4 log₁₀cp/mL will be also considered although 2.33 log₁₀cp/mL is used to determine the analysis set defined in [Section 5.4](#).

Table 5. Rules of Viral Titers

Reported Value	RT-qPCR	
	Treated as	Categorized as
\geq Negative threshold	Reported value	Positive
< Negative threshold	Negative threshold	Negative
Negative	Negative threshold	Negative

Abbreviations: RT-qPCR= reverse transcription-quantitative polymerase chain reaction.

Duration (days) of viral shedding will be calculated as (Date/Time of post-baseline last positive sample – Date/Time of study drug administration).

AUC of viral level is calculated from date/time of study drug administration to date/time of last measurable value of patients who have at least one post-baseline result using linear trapezoidal rule. Viral level at baseline will be considered as result at study drug administration.

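### Viral-load AUC ends at each patient's own last value, so an early dropout with high viral load can score lower than a fast clearer followed to Day 28

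*SAP*

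**What the plan says.** SAP 11.1.1 holds the only definition. Protocol 7.8.5.2 names AUC of viral levels but does not define it.

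- **Span:** "AUC of viral level is calculated from date/time of study drug administration to date/time of last measurable value".
- **Who and how:** patients with "at least one post-baseline result using linear trapezoidal rule". At time zero, "Viral level at baseline will be considered as result at study drug administration".
- **Floor:** the rules in SAP Table 5 set out "how viral titers will be treated in descriptive summary and AUC calculation". A negative result, or one below the threshold, is entered at the threshold rather than at zero.
- **Thresholds:** "The analysis will be based on the 2.33" log10 cp/mL. "Additionally negative threshold for 3 and 4" log10 cp/mL will be considered.
- **Reporting:** "AUC of viral levels will be summarized by each treatment group at each scheduled visit using descriptive statistics". No cumulative AUC per visit is defined.

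The section gives no common end day, division by time, minimum follow-up or rule for early withdrawal, and it does not define *last measurable value*. Part 2 swabs fall on Days 1, 3, 7, 10, 14, 21 and 28, with Day 90 only if Day 28 is positive (Protocol 6.4, Table 6-3). Patients who are dosed and then discontinue are not replaced (Protocol 4.2.1), so partial profiles stay in the data.

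**The concern.** An area under a curve compares patients fairly only if it covers the same period for each of them. Here the end time belongs to the patient, and the floor makes time itself add area. A cleared patient who stays in the study goes on accumulating at the threshold, while a patient who leaves with a high viral load stops. A low AUC can therefore mean fast clearance or early departure.

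At stake is the reading of the arm summaries of AUC. If dropout differs between CT-P59 and placebo, part of the difference in mean AUC reflects follow-up and not viral burden. Other endpoints in the SAP have rules for this. Time to clinical recovery has explicit rules for death and withdrawal (SAP 9.2), and these extend to the other time-to-event endpoints (SAP 9.3). Negative conversion has a rule for missing swabs, and the secondary efficacy endpoints are assessed to Day 14 and Day 28 (SAP 9.3).

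**Working it through.** The documents state no AUC value, so there is no figure to reproduce. I applied the stated rule to illustrative profiles.

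**Inputs.** From the documents: swabs at 0, 2, 6, 9, 13, 20 and 27 days after dosing (Protocol Table 6-3), the linear trapezoid, and a floor of 2.33 (SAP 11.1.1). Assumed: the log10 viral loads below, and that AUC is taken on the log10 scale, which the thresholds imply but the SAP does not state.

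- Fast clearer, followed to Day 28: 7, 5, 3, then 2.33 at every later swab.
- Slow clearer, last swab Day 10: 7, 6.5, 5.5, 4.5.
- The same slow course followed to Day 28: 7, 6.5, 5.5, 4.5, 3.5, 3, 2.6.

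**Reading A: end at the last available result.** Each interval adds (mean of its two values) × (days).

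- Fast: 12 + 16 + 7.995 + 9.32 + 16.31 + 16.31 = 77.9. Of this, 18 × 2.33 = 41.9 (54%) accrues after the first negative swab.
- Slow, leaves after Day 10: 13.5 + 24 + 15 = 52.5.
- Slow, completes: 52.5 + 16 + 22.75 + 19.6 = 110.9.

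The dropout (52.5) scores below the fast clearer (77.9). Over the same nine days the order is right: 12 + 16 + 7.995 = 36.0 for the fast clearer against 52.5.

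**Higher thresholds.** At 3 the fast clearer scores 28 + 21 × 3 = 91.0. At 4 the Day 7 value is also floored, giving 12 + 18 + 21 × 4 = 114.0. The dropout stays at 52.5, so the gap widens with no change in virology.

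**Visit window.** Day 28 allows ±3 days. For a cleared patient that alone moves AUC by 3 × 2.33 = 7.0 either way.

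**Reading B: end at the last value at or above the threshold.** The fast clearer stops at Day 7 with 12 + 16 = 28.0 against 52.5, so the order is correct. Truncation remains: the slow clearer last swabbed on Day 3 scores 13.5, below 28.0.

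**Arm means under reading A.** Suppose both arms follow the slow course and differ only in the fraction leaving after Day 10. The spurious shift is (difference in dropout) × (110.85 − 52.5) = difference × 58.35.

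| Extra dropout in one arm | Shift in mean AUC |
|---|---|
| 1 percentage point | 0.6 log-days |
| 5 percentage points | 2.9 log-days |

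For scale, the fast and slow completers differ by 110.85 − 77.94 = 32.9.

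**Spread between patients under reading A.** A simulation of 20,000 patients per scenario assumed baseline 6 ± 1.3 log10, median decline 0.33 log10 per day and Day 28 swabs spread over their window. Follow-up length explained 4% of the AUC variance at 0% dropout, 12% at 2%, 25% at 5%, 38% at 10% and 53% at 20%. On untransformed cp/mL it explained about 0%.

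**Dividing by time covered.** Fast 77.9/27 = 2.9 and dropout 52.5/9 = 5.8, so the order is restored. But the same slow course scores 5.8 if the patient leaves and 110.85/27 = 4.1 if the patient stays, which is 42% higher only because of leaving.

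**The case against.** **The term may mean the last positive value.** The protocol's pharmacokinetic AUC runs to the last quantifiable concentration (Protocol 7.4.1), and *measurable* could be meant in that sense. The worked reversal then disappears. This stands as a real ambiguity. Against it, the same SAP section refers to the last positive sample when it defines duration of shedding, which favours the last available result for AUC. Under either reading the end time differs by patient.

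**The by-visit summary may imply common windows.** A cumulative AUC to each visit would give them. But the same list includes duration of shedding, which is one value per patient, so the phrase cannot apply literally to every item, and no per-visit AUC is defined.

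**Completers share about 27 days.** This stands. A reader might infer that the AUC mainly measures length of follow-up. That is not shown: among completers the floor contribution is nearly constant and largely cancels between arms. In the simulation follow-up dominated the variance only at about 20% dropout, and the documents give no dropout rate.

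**Day 90.** A reader might infer that patients positive on Day 28 have their AUC extended by 62 days. In the illustration, a negative Day 90 swab would add (2.6 + 2.33)/2 × 62 = 152.8 and take 110.9 to 263.7. The text does not favour that reading. The sentence beginning "If EOT result is available and the result from patient whose viral titer result at Day 28" lists the summaries that take the EOT result, and AUC is not among them. SAP section 5 keeps EOT and unscheduled visits out of visit-based tables unless otherwise specified. SAP section 2 limits scheduled data in the Day 28 report to Day 28 for ongoing patients. What remains is that the AUC sentence has no cut-off of its own, so the final report would benefit from one.

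**Consequence.** AUC is exploratory, no test is planned for it, and viral results by visit are reported beside it. This stands.

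**Conclusion.** The concern holds as a minor point. The stated rule gives AUCs over unequal periods, and on the plain reading it can rank an early dropout with high viral load ahead of a fast clearer (52.5 against 77.9 log-days in the illustration). At arm level the distortion depends on dropout and needs it to differ between arms: about 0.6 log-days per percentage point of extra Day 10 dropout in the example. It is small if nearly all patients reach Day 28.

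This rests on assumed viral-load courses, the log10 scale and the last-available-result reading. Under the last-positive reading the headline reversal goes, and truncation of early leavers remains. It would be too strong to say that the rule fails equally under both readings, or that differences in dropout will be seen as drug effects. No primary or key secondary conclusion changes.

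**What to change.** In SAP 11.1.1:

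1. Compute AUC on the log10 scale over two fixed windows, dosing to Day 14 and dosing to Day 28, and state how a swab taken off the nominal day is handled.
2. Summarise each window in patients with a swab at or near its end, and report the number of incomplete profiles by arm.
3. Give the time-weighted average (AUC divided by time covered, or its change from baseline) as a sensitivity analysis for incomplete profiles. Note that it over-weights early high values in patients who leave, so it should not replace the fixed window.
4. Define *last measurable value*.
5. State that Day 90 (EOT) and unscheduled swabs do not enter AUC.

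The cost is a few sentences and minor programming. Some patients will be left out of the longer window, which is why the counts by arm should be shown.

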11.1.2. Genotype of SARS-CoV-2 Viral Isolates

Genotype result will be summarized on the ITTI Set by each treatment group at each scheduled visit using frequency table and will be presented in listing.

11.1.3. Viral Serology for SARS-CoV-2 Antibody

Viral serology for SARS-CoV-2 antibody test with assays detecting serum antibodies against SARS-CoV-2 will be performed locally using the serum samples (if the assay is available). Viral serology for SARS-CoV-2 antibody result will be summarized on the ITTI Set by each treatment group at each scheduled visit using frequency table.

12. Changes in the Planned Analysis

- For patients who had negative result at Day 1 or missing Day 1 result of RT-qPCR, the ITTI Set will also include these patients if they are confirmed SARS-CoV-2 infection positive by Day 2 or Day 3. These patients can also be considered as infected since the virus was detected at Day 2 or Day 3.
- All expression or text regarding phenotype will be deleted in SAP since phenotype was not analyzed.

13. Reference List

International Council for Harmonisation (ICH) Assembly. ICH E9: Statistical principles for clinical trials – Step 5. 01 September 1998.

US Department of Health and Human Services. (2010). National Institutes of Health, National Cancer Institute. Common Terminology Criteria for Adverse Events (CTCAE) Version 5.0. Available from: <http://evs.nci.nih.gov/ftp1/CTCAE/About.html>.

Chan, I. S. F., and Zhang, Z. (1999). Test-Based Exact Confidence Intervals for the Difference of Two Binomial Proportions. Biometrics 55:1202–1209.

Schoenfeld, D. (1981). The asymptotic properties of nonparametric tests for comparing survival distributions. Biometrika. 68 (1): 316–319.

CDER, CBER, Multiple Endpoints in Clinical Trials. Guidance for Industry. Draft Guidance. January 2017. Available from: <https://www.fda.gov/files/drugs/published/Multiple-Endpoints-in-Clinical-Trials-Guidance-for-Industry.pdf>

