1.2 CT-P59

CT-P59 is a human monoclonal antibody targeted against SARS-CoV-2 spike protein as a treatment for SARS-CoV-2 infection, which is manufactured by recombinant deoxyribonucleic acid technology in a Chinese hamster ovary mammalian cell line. The dosage form of CT-P59 is solution concentrate for dilution for administration in a single intravenous (IV) infusion.

The main mechanism of action is blocking the binding between SARS-CoV-2 RBD and cellular receptor, ACE2, thus inhibiting their infection to host cells. Although it has been known in many virus infections that antibodies can remove the virus-infected cells via antibody Fc-dependent function such as antibody-dependent cellular cytotoxicity, it is unlikely that CT-P59 induces antibody Fc-dependent virus clearance, considering the life cycle of SARS-CoV-2, which is assembled inside cells and released via exocytosis. However, it is postulated that there are additional mechanisms of CT-P59 mediated virus clearance by opsonization and complement activation (i.e., antibody-dependent, complement-dependent virolysis or antibody-dependent phagocytosis).

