In Study CT-P59 3.2 Part 1, the efficacy of the proposed clinical regimen (40 mg/kg) and a higher regimen (80 mg/kg) were evaluated in patients with mild to moderate COVID-19 and overall, the study provided evidence that CT-P59 is effective for the treatment of mild to moderate COVID-19 patients. In particular, a potential benefit was seen for the primary endpoint of proportion of patients with clinical symptom requiring hospitalization, oxygen therapy, or experiencing mortality due to SARS-CoV-2 infection up to Day 28, which is clinically meaningful and is considered as both an individual patient benefit and public health benefit. Clinical efficacy data did not show a dose-response relationship for CT-P59 treatment. Viral shedding results from Studies CT-P59 1.2 and CT-P59 3.2 Part 1 were also suggestive of a relatively flat dose-response relationship. In addition, clinical safety showed that treatment-emergent adverse events (TEAEs) were comparable across CT-P59 and Placebo treatment groups. The majority of TEAEs were mild to moderate in severity and most events were singular and without associated dose-dependence.

Pharmacodynamic/PK analyses support the 40 mg/kg dose of CT-P59. The serum concentration of CT-P59 in human lung tissues was estimated using antibody distribution coefficients. Shah and Betts found that typically the concentration of monoclonal antibody in lung is 15% (Shah *et al*, 2013). Based on this, the CT-P59 40 mg/kg dose is expected to achieve approximately 14.9 µg/mL (99.5 µg/mL x 0.15) of serum concentration in lung tissue at 28 days after study drug administration in mild to moderate COVID-19 patients. The estimated serum concentration is above the in vitro EC90 value (25.09 ng/mL) of viral neutralization.

In conclusion, based on the clinical data from Studies CT-P59 1.1, CT-P59 1.2 and CT-P59 3.2 Part 1, a single dose of 40 mg/kg is considered as the appropriate dosing regimen to treat patients with mild to moderate COVID-19 in Part 2 of Study CT-P59 3.2.

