5.2.1 Identity of CT-P59

CT-P59 is a monoclonal antibody which is being developed by the sponsor as a potential treatment for SARS-CoV-2 infection.

CT-P59 is supplied as a sterile, preservative-free solution of SARS-CoV-2 RBD binding monoclonal antibody in a 20 mL single use vial for IV infusion. CT-P59 is a clear to opalescent, colorless to pale yellow solution for injection, with a pH of 6.0 and 960 mg of SARS-CoV-2 RBD binding monoclonal antibody in 16 mL for IV infusion. One vial (16 mL) delivers 960 mg SARS-CoV-2 RBD binding monoclonal antibody, 13.12 mg of L-histidine, 15.84 mg of L-histidine monohydrochloride monohydrate, 8.0 mg of polysorbate 80, 505.584 mg of L-Arginine monohydrochloride, and water for injection. The container closure system includes type I borosilicate glass vial, Fluroetec Film coated rubber stopper and flip-off type aluminum cap.

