6.4 Virology and Serology Assessments

Viral shedding based on RT-qPCR or cell culture, genotyping and phenotyping of SARS-CoV-2 isolates will be performed using the nasopharyngeal swab samples for all patients.

Samples will be secured at the central laboratory for analysis and backup samples will be retained. Viral serology for SARS-CoV-2 antibody test with assays detecting serum antibodies against SARS-CoV-2 will also be performed locally using the serum samples (if the assay is available). The sample for virology and serology assessments will be collected for analysis at the time points specified in [Table 11-1](#) and [Table 11-2](#).

Details of biologic sampling time points and acceptable tolerance windows for virology assessments are described in [Table 6-2](#) and [Table 6-3](#).

Table 6-2 Nasopharyngeal Swab Sampling Time Points for Virology Assessment – Part 1

Day	Time point	Window
Day 1	Pre-dose	Pre-dose within the day
Day 2	24 hours after start of infusion	± 4 hours
Day 3	48 hours after start of infusion	
Day 4	72 hours after start of infusion	
Day 5	96 hours after start of infusion	
Day 6	120 hours after start of infusion	
Day 7	144 hours after start of infusion	
Day 10	216 hours after start of infusion	
Day 14	312 hours after start of infusion	± 1 day
Day 17	384 hours after start of infusion	
Day 21	480 hours after start of infusion	
Day 28*	648 hours after start of infusion	± 3 days

Abbreviation: RT-qPCR = reverse transcription quantitative polymerase chain reaction; SARS-CoV-2 = severe acute respiratory syndrome coronavirus 2

*If the RT-qPCR result on Day 28 shows positive of SARS-CoV-2 infection, additional viral shedding will be conducted on Day 90.

Table 6-3 Nasopharyngeal Swab Sampling Time Points for Virology Assessment – Part 2

Day	Time point	Window
Day 1	Pre-dose	Pre-dose within the day
Day 3	48 hours after start of infusion	± 4 hours
Day 7	144 hours after start of infusion	
Day 10	216 hours after start of infusion	
Day 14	312 hours after start of infusion	± 1 day
Day 21	480 hours after start of infusion	
Day 28*	648 hours after start of infusion	
		± 3 days

Abbreviation: RT-qPCR = reverse transcription quantitative polymerase chain reaction; SARS-CoV-2 = severe acute respiratory syndrome coronavirus 2

*If the RT-qPCR result on Day 28 shows positive of SARS-CoV-2 infection, additional viral shedding will be conducted on Day 90.

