 - A patient will be considered to have moderate disease severity if the question “Are there any radiological findings of pneumonia and clinical signs of pneumonia?” is answered ‘Yes’ on the ‘Radiography’ page of eCRF at the screening visit.

- Day1 serostatus (Sero Positive, Sero Negative and Other):
 - A patient will be considered to have seropositive serostatus if there is at least one positive result of viral serology for SARS-CoV-2 Antibody IgG and IgM at Day 1.
 - A patient will be considered to have seronegative serostatus if there are both negative results of viral serology for SARS-CoV-2 Antibody IgG and IgM at Day 1.
 - Otherwise, a patient will be considered to have other serostatus.

Demographics and stratification details will be listed for the ITT Set by treatment group.

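### Where local kits detect spike antibody, the post-dose serology table in SAP 11.1.3 will count infused CT-P59 as a positive result in the active arm

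*SAP*

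**What the plan says.** **The drug.** Protocol section 1.2: "CT-P59 is a human monoclonal antibody targeted against SARS-CoV-2 spike protein as a treatment for SARS-CoV-2 infection". Protocol section 5.2.1 gives the binding region; a vial holds "960 mg of SARS-CoV-2 RBD binding monoclonal antibody in 16 mL for IV infusion".

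**Its level after dosing.** Protocol section 1.3.2 expects the 40 mg/kg dose to achieve "approximately 14.9 µg/mL (99.5 µg/mL x 0.15) of serum concentration in lung tissue at 28 days after study drug administration". The serum input to that lung estimate is therefore 99.5 µg/mL.

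**The test.** Protocol section 6.4 describes the serology only as a test "with assays detecting serum antibodies against SARS-CoV-2 will also be performed locally using the serum samples", at sites that have an assay. SAP section 11.1.3 repeats this. Neither document states the target antigen or asks for a kit that does not react with CT-P59.

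**The visits.** SAP Appendix 1 schedules serology before dosing on Day 1 and then on Days 7, 14, 28, 56 and 90.

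**The analysis.** SAP section 11.1.3: "Viral serology for SARS-CoV-2 antibody result will be summarized on the ITTI Set by each treatment group at each scheduled visit using frequency table". Protocol section 7.8.5.2 had planned only a data listing for serology. SAP section 12 records two changes to the planned analysis (the ITTI definition and the removal of phenotype); this one is not among them.

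**Antibody class.** IgG and IgM are named only in SAP section 7.1, where Day 1 seropositivity means "at least one positive result of viral serology for SARS-CoV-2 Antibody IgG and IgM at Day 1".

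The objective served, in SAP section 3.4, is exploratory.

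**The concern.** The test is described as one for antibodies against SARS-CoV-2, and the study drug meets that description. A kit that captures spike/RBD antibody of the drug's class can turn positive because the patient was infused, whether or not the patient has made any antibody. This can happen in one arm only and in one direction only.

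At stake is what a by-arm table can tell a reader. The CT-P59 arm could appear to seroconvert earlier and more often for no reason other than the infusion. A true reduction of the patients' own response under treatment could be hidden or even reversed. Nothing in the plan identifies which results are affected. The first Part 2 study report takes data up to Day 28 (SAP section 2), so the post-dose serology in it comes from the period of highest drug level.

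**Working it through.** **1. Reproduce the protocol's figure.** 99.5 × 0.15 = 14.925, which rounds to the stated 14.9 µg/mL. The 99.5 µg/mL serum level can be taken as the protocol's own.

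**2. Scale.** The same section gives an EC90 of 25.09 ng/mL. 99,500 / 25.09 ≈ 3,966. This shows that the level is large relative to activity in vitro. EC90 is a neutralization value and not a kit's detection limit, so the ratio says nothing direct about kit positivity.

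**3. Is drug still present at the later visits?** Table 1-1 of the protocol gives simulated healthy-subject AUCs at 40 mg/kg of 40,364 µg·h/mL to 72 h and 68,952 µg·h/mL to 168 h.

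- Mean level over 72–168 h: (68,952 − 40,364) / 96 = 297.8 µg/mL, placed at the midpoint, day 5.
- Apparent half-life from there to 99.5 µg/mL at day 28: ln 2 × (28 − 5) / ln(297.8 / 99.5) ≈ 14.5 days.
- Level at day d: 99.5 × 2^(−(d − 28)/half-life).

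| Half-life (days) | Day 56 (µg/mL) | Day 90 (µg/mL) |
|---|---|---|
| 10 (assumed) | 14.3 | 1.4 |
| 14.5 (derived) | 26.2 | 5.2 |
| 21 (assumed) | 39.5 | 12.9 |

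This joins simulated healthy-subject exposure to a level quoted for patients and assumes mono-exponential decline, so it is indicative only. On that basis, drug is expected at every post-dose serology visit.

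**4. Size of the bias.** Let s be the patients' own seropositivity, taken as equal in both arms, and f the share of patients tested with a kit that reads the drug as positive. Apparent positivity on CT-P59 is s + f(1 − s), so the spurious excess over placebo is f(1 − s). The documents give neither s nor f; both are assumed here. Excess in percentage points:

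| s | f = 0 | f = 0.25 | f = 0.5 | f = 1 |
|---|---|---|---|---|
| 30% | 0 | 17.5 | 35 | 70 |
| 60% | 0 | 10 | 20 | 40 |
| 80% | 0 | 5 | 10 | 20 |
| 95% | 0 | 1.3 | 2.5 | 5 |

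**5. Masking of a real effect.** Suppose true seropositivity is 90% on placebo and 60% on CT-P59 (assumed), a difference of −30 points.

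- f = 0.5: 60 + 0.5 × 40 = 80%, shown as 80 − 90 = −10 points.
- f = 1: 60 + 1 × 40 = 100%, shown as 100 − 90 = +10 points.

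The sign of the displayed difference then depends on a mix of kits that neither document asks to be recorded.

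**The case against.** The best defence is that the SAP promises very little. It says that results will be summarized. It defines no seroconversion endpoint, test, confidence interval or formal contrast between arms, and it does not say that the table represents the patient's own response. That stands. A reader might infer that the SAP presents the table as host response, or that it merges IgG with IgM after dosing. The documents support neither inference: section 11.1.3 is silent on both, and the table shells and laboratory manual are not before us. What can be said is that no separation is specified.

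Second, the bias depends on kit type. A nucleocapsid kit should not detect an RBD-binding antibody, so the bias could be nil. That also stands, and it is why the range starts at zero. It does not remove the point, because the plan neither excludes reactive kits nor identifies them.

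Third, IgM is not certain to be clean. A drug of class IgG should not register on an IgM-specific result, but IgG1 appears only in the protocol's abbreviation list, and the text calls CT-P59 a human monoclonal antibody without giving its class. The class needs confirming before IgM is relied on.

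Fourth, the reach is small and the remedy could outgrow it. Part 2 plans about 106 centers in 19 countries, so collecting kit targets takes work. That argues for a labelled table first, with display by antigen only where the information can be had.

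**Conclusion.** The point holds in conditional form. Wherever a local kit detects spike/RBD antibody of the drug's class, post-dose positives in the CT-P59 arm will include infused drug, and the planned table cannot separate carry-over from host response. The excess is f(1 − s): zero if no kit reacts with the drug, and 1.3 to 70 percentage points across the assumed non-zero range of f (0.25 to 1) and s (30% to 95%). The formula assumes that a reactive kit reads every dosed patient as positive at the visit in question.

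Two stronger readings are tempting. One is that the serology objective is confounded outright; the documents do not support this, because the kit antigen is not given. The other is that a level some 4,000 times EC90 guarantees near-universal positivity on drug; this does not follow, because EC90 is not an assay threshold.

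The reach is one exploratory descriptive table. Day 1 serology is drawn before dosing, so baseline serostatus stands. The placebo arm receives no antibody. The primary and key secondary analyses do not use post-dose serology.

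**What to change.** In SAP section 11.1.3:

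- Tabulate IgG and IgM separately at each visit where both are reported.
- Add a footnote that post-dose CT-P59-arm results from spike/RBD-reactive or unknown-target assays may include study drug and are not to be read as host seroconversion.
- Where a kit's target antigen can be obtained before unblinding, show results by antigen and base any post-dose reading across arms on assays that do not detect CT-P59. Use IgM for this only if the drug is confirmed to be IgG.

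In SAP section 12, list the change from the protocol's data listing to a frequency table.

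The class split, the footnote and the section 12 entry cost only SAP and table-shell wording. Collecting kit targets takes some effort from sites, and fewer results will support a post-dose reading across arms. No new samples or visits are needed, and the Day 1 serostatus definition is unchanged.
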